Recruitment. Our intended sample size across both conditions is N=180 (MEET-ME, n=120; NHTP, n=60). We include a 2:1 ratio so we may increase our ability to examine the MEET-ME condition in greater detail. Candidates must (1) be male at birth and identify as male, (2) be between the ages of 18 and 24 (inclusive), (3) self-report as single, (4) self-report as HIV-negative, (5) speak and read English, and (6) report UAI with a male partner in prior 6 months. Consistent with the Internet's potential reach, we will allow YMSM from around the country to participate in the intervention. We will reach the population using social media ads on Facebook and Twitter. Promotional materials will describe the study and provide a 1-800 number to call to verify eligibility. Once determined eligible, YMSM will receive a code to access the site.

Once YMSM enter our website, we will verify that participants live in the US using the American Registry for Internet Numbers (ARIN) regional IP codes and zip codes. Participants will complete a 30 minute baseline questionnaire and be randomized in a 2:1 ratio into the MEET-ME or NHTP site. As part of the baseline questionnaire, we will ask participants to provide information that may help us contact them for FU assessments and verify that they are not fraudulent or duplicate entries^{87,88}. We will use best practices^{89,90} to retain participants (e.g., comprehensive locator information that includes participants' cell phone number, e-mail, Facebook and/or Skype username, and contact information for 2 peers who could help us contact them).

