Psychological risk correlates. We will measure *depression*, *anxiety*, and *loneliness* symptoms as markers of psychological distress. Depression and anxiety symptoms in the past week will be measured using the Brief Symptom Inventory¹⁰⁵. Both scales include 6 items rated on a 5-point scale (1=never, 5 = very often), respectively. We will use the UCLA Loneliness scale¹⁰⁶ to measure feelings of loneliness (1=Never;4=Often). We will also measure *self-esteem* using Rosenberg’s scale¹⁰⁷, a 10-item measure using a 5-point scale. We will measure *internalized homophobia*¹⁰⁸ with 12 items measured on a 4-point scale (0=Strongly disagree; 3=Strongly agree). Finally, we will measure *sexuality-related stressors* using a 9-item scale (0=never/4=3+ times) with strong reliability¹⁰⁹ assessing the frequency of discriminatory events (e.g., verbal insults) due to someone knowing/assuming YMSM were gay/bisexual.

Data Analyses. Prior to conducting our multivariate analyses, we will examine study variables using descriptive statistics and test for differences across demographic characteristics (e.g., race/ethnicity, age, education) using t-tests, ANOVAs, and Chi-squares, as appropriate. As participants will be randomized to the two treatment groups, systematic baseline differences are not expected; however, in the event that some parameters differ across conditions at baseline, they will be included as covariates in subsequent multivariate models. We will calculate descriptive summary statistics corresponding to the study variables at each visit to understand any temporal patterns, as well as compare the two treatment groups in terms of average change from baseline after intervention (averaged across all three FU times).

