Estimation of parameters for a subsequent R01. Consistent with the R34 mechanism, the primary role of this pilot RCT is to ensure that the critical parameters required to plan a large trial are estimated as informatively as possible. Certain principles then follow: (1) If alterations are necessary to address measurement or performance problems, these will be permitted in an effort to establish optimal procedures and design parameters before a future trial, precisely so that no changes in protocol will be required during a future trial; and, (2) Estimation of critical design parameters with point and confidence interval estimates will be considered highly important, as large sample sizes are not required to locate these parameters adequately when planning for a subsequent trial. As a result, we are not powered to estimate small effect sizes or carry out sophisticated statistical analyses; rather, we seek to estimate key study parameters with sample means and proportions together with two-sided 95% confidence intervals, and test the primary null hypotheses at the

traditional two-sided level $\alpha=.05$.

To test for intervention effects over time with pilot RCT data, we will use the general framework of generalized

linear mixed models (GLMM) to model the longitudinal outcome trajectories¹¹⁰⁻¹¹². Note that some of our outcomes

are binary, some count and some continuous traits and thus need to be treated differently. The general form of the GLMM will be $(\mu_{ij}) = \beta_{0i} + \beta_{cov} Covariates_{ij} + \beta_{visit} Visit_j +$

Table 4. Detectable Effect (.80 power, alpha=.05)	N = 140	N = 160	N = 180
Continuous Outcomes			
Within-subject correlation (rho=.4)	.39	.35	.33
Within-subject correlation (rho=.5)	.41	.38	.35
Within-subject correlation (rho=.6)	.44	.40	.37
Binary Outcomes (p(NTHP)=.40)			
Within-subject correlation (rho=.4)	2.19	2.04	1.93
Within-subject correlation (rho=.5)	2.31	2.14	2.02
Within-subject correlation (rho=.6)	2.43	2.24	2.11

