$\beta_{Trt} Trt_i + \beta_{Trt \times visit} rt_i \times Visit_j$, where μ_{ij} is the mean response corresponding to subject *i* on visit *j* (*baseline and three follow-ups*), *g* denotes the link function (identity for continuous outcome, logit for binary outcome and natural log for count outcomes); $Trt_i = 1$ if the *i*-th subject is in the MEET-ME group and 0 if the *i*-th subject is in the NTHP group. The variable Visit can be coded in different ways depending upon how one wants to model the effect of time on the mean response. For example, for characterizing only pre vs. post effect Visit can be coded as a binary indicator with 0 representing baseline and 1 representing post-randomization; Assuming a linear time trend, Visit can be coded as 0, 1, 2, 3, or it can be simply coded as a categorical variable representing the distinct effect of each visit compared to the baseline. The interaction coefficients $\beta_{Trt \times Visit}$ are of interest here, measuring the difference in the rate of change in outcome across the two treatment groups at each visit. If the baseline outcome measure is included as a part of the covariates on the right hand side of the

NCT02842060

above equation, then we only have three repeated measures on the left hand side of the model ($j=1,2,3$) and we can look at average treatment effect across visits without including the $Trt \times Visit$ interaction term. In this particular case, the GLMM analysis with continuous outcome will be equivalent to a repeated measures analysis of covariance after adjusting for baseline values. The subject-specific random intercepts β_{0i} are assumed to be normally distributed with a common variance and they account for within-person correlation. We will also explore if we need a subject specific random-slope corresponding to visit in the above model. Maximum likelihood estimation will be used for fixed effect parameters. Models will be compared according to information criterion like AIC, BIC. For some binary outcomes like STI/HTV testing, we will perform an aggregate analysis after collapsing across the repeated measures using simple logistic regression comparing whether the probability of having tested at least once over the entire FU period is different across treatment groups, after adjusting for baseline values. To ensure robustness, we will also apply an exchangeable working correlation structure to its corresponding generalized estimating equation (GEE) model.

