Power for primary analysis: As shown in Table 4, we will have 80% power to detect a medium intervention effect (Cohen's $d > .35$) at $\alpha=.05$ in a continuous measure using a repeated measures group design (N=180) with 4 observations (baseline + 3 FUs) when the standard deviation is 1 and the correlation between observations on the same subject (ρ) is 0.6. For dichotomous outcomes, we estimate 80% power at $\alpha=.05$ to detect an odds ratio of 2.11 or greater assuming that the proportion for the intervention condition is .58 and the attention-control condition is .40, with ρ also being .60. We note that there is some controversy regarding the use of "pilot data" to estimate the actual effect size, as specified by Kraemer et al.¹¹³. We agree with their view that clinically meaningful effect sizes should be decided based on extrinsic, clinical judgment grounds, and not based on the pilot data which are too few, typically, to obtain reliable conclusions. However, we can use these data to rule out unusually large or small effects through standard 95% confidence interval procedures. Thus, we will confirm that extrinsic effect sizes are contained within our confidence intervals¹¹³ and use these Even with 20% attrition, we will have preliminary effects with adequate error margins to inform the subsequent trial.

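### For continuous outcomes, the mixed model's stated effect of interest is a change-from-baseline contrast, and the more precise baseline-adjusted form, already described, is not made primary

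*Combined protocol and SAP*

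**What the plan says.** The relevant text is in Data Analyses and in the section after it, Estimation of parameters for a subsequent R01.

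- **Descriptive step (Data Analyses).** Before the multivariate models, the plan gives summary statistics by visit and will "compare the two treatment groups in terms of average change from baseline after intervention (averaged across all three FU times". The same paragraph adds that "in the event that some parameters differ across conditions at baseline, they will be included as covariates in subsequent multivariate models". It does not name the baseline value of the outcome among those parameters.
- **General mixed model (Estimation of parameters).** This is the model that tests intervention effects. Baseline and the three follow-ups are all responses. The model has a random intercept, a treatment main effect, a visit effect and their interaction. Visit may be coded as pre/post, as a linear trend or as categories. The interaction coefficients "are of interest here, measuring the difference in the rate of change in outcome across the two treatment groups at each visit".
- **Baseline-adjusted form (same section).** A conditional sentence then describes moving the baseline outcome to the covariates. This leaves three responses and an average treatment effect without the interaction, and the plan itself calls it equivalent to repeated measures analysis of covariance. It is not tied to baseline imbalance, and it is not declared primary.
- **HIV/STI testing (same section).** The analysis collapsed over follow-up is a logistic regression adjusted for baseline without any condition.

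**The concern.** A change score subtracts the whole baseline value. When the correlation between visits is only .4 to .6, the best prediction of follow-up from baseline uses only that fraction of it, so full subtraction adds baseline noise to the treatment effect. The interaction that the plan singles out carries this cost for a continuous outcome; the alternative described a few lines later does not.

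The plan gives no rule for choosing between them. Its reference to AIC and BIC cannot settle the matter, because one form models four responses per man and the other three, and such criteria are not comparable across different response data.

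The stake is precision. The plan says that the pilot's main role is to estimate design parameters as informatively as it can, with 95% intervals. A needlessly wide interval for the effect works against that aim.

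**Working it through.** **Inputs.** Recruitment (Phase 3): "Our intended sample size across both conditions is N=180 (MEET-ME, n=120; NHTP, n=60". Power for primary analysis: a design "with 4 observations (baseline + 3 FUs) when the standard deviation is 1". Table 4: 80% power, α = .05, within-person correlation ρ = .4, .5, .6. The test is two-sided (Estimation of parameters). Equal correlation between all visits follows from the random-intercept model for a continuous outcome. The multiplier is 1.960 + 0.842 = 2.802, and 1/120 + 1/60 = .025.

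**1. The plan's own figure.** Table 4 gives .33/.35/.37 for continuous outcomes at N = 180. The formula d = 2.802 × √[(1+3ρ)/4 × .025] gives .3285/.3502/.3706, which matches. This is the variance of a simple mean of all four observations, baseline included, so Table 4 describes neither model form.

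**2. Change contrast.** For the mean of three follow-ups minus baseline, the variance per man is (1+2ρ)/3 + 1 − 2ρ = 4(1−ρ)/3.

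**3. Baseline-adjusted mean of three follow-ups.** The variance per man is (1+2ρ)/3 − ρ² = (1−ρ)(1+3ρ)/3.

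**4. Comparison.** The ratio is 4/(1+3ρ), and the share of information lost is 1 − (1+3ρ)/4. Detectable d is 2.802 × √(variance × .025).

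| | ρ = .4 | ρ = .5 | ρ = .6 |
|---|---|---|---|
| Variance, change | .800 | .667 | .533 |
| Variance, adjusted | .440 | .417 | .373 |
| Ratio | 1.82 | 1.60 | 1.43 |
| Standard error larger by | 35% | 26% | 20% |
| Information lost | 45% | 38% | 30% |
| Detectable d, change, 120:60 | .40 | .36 | .32 |
| Detectable d, adjusted, 120:60 | .29 | .29 | .27 |
| Detectable d, change, 96:48 | .44 | .40 | .36 |
| Detectable d, adjusted, 96:48 | .33 | .32 | .30 |
| Power at d = .35, change, 120:60 | 70% | 77% | 86% |
| Power at d = .35, adjusted, 120:60 | 92% | 93% | 95% |

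The 96:48 rows apply the plan's projected 20% attrition to both arms (144 men) and replace .025 by 1/96 + 1/48 = .03125.

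**5. Does the loss reach the mixed model?** Generalised least squares on the general model (four responses, treatment main effect, interaction) gives the same ratios, 1.82/1.60/1.43. This holds for the pre/post interaction and for the average of the three categorical-visit interactions. Simulation of 20,000 trials at 120:60 gave 1.84 at ρ = .4 and 1.43 at ρ = .6.

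**6. Single-visit interaction.** The variances are 2(1−ρ) for change and 1−ρ² for the adjusted form. The ratio is 2/(1+ρ) = 1.43/1.33/1.25, an excess of 43/33/25%.

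**7. Chance imbalance.** The gap between steps 2 and 3 is exactly (1−ρ)²: .80 − .44 = .36, .667 − .417 = .25, .533 − .373 = .16. A baseline difference of .2 SD moves the change estimate by .2(1−ρ) = .12/.10/.08 SD relative to the adjusted one. A difference larger than .2 SD has probability 2[1 − Φ(.2/√.025)] = 21%. This explains where the excess variance comes from; it is not a further loss.

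**The case against.** The strongest reply is that the plan does not commit to a change-score analysis. A reader might join the average-change sentence to the covariate rule and infer that efficacy is judged on raw change, with the baseline outcome adjusted for only when the arms happen to differ on it. The documents do not support that. The average-change sentence belongs to the descriptive step. The covariate rule speaks of unnamed parameters, after a sentence about demographic characteristics. The analysis of covariance form does not depend on imbalance, and if it is used the loss is zero.

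Even if that rule were taken to cover the baseline outcome, 82/60/43% would overstate the loss. Suppose that differing means two-sided p < .05 (an assumption; the plan gives no criterion). The part of the imbalance variance left unadjusted is then .95 − 2 × 1.96 × .0584 = .721. The excess becomes .721 × (1−ρ)² / adjusted variance = 59/43/31%.

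Three further objections stand in part.

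- **Scope.** The plan uses log and logit links for some outcomes, and the HIV/STI testing analysis is already baseline-adjusted. The figures therefore do not apply to all three primary outcomes alike. Outcome indicators does label condom use and number of UAI partners and occasions continuous, but the UAI figures may be modelled as counts.
- **Power at ρ = .6.** This is the value in the power paragraph. There the change contrast detects .32, smaller than Table 4's .37. At ρ = .5 it is .36 against .35; only at ρ = .4 (.40 against .33) is it clearly worse than Table 4. It cannot be inferred that the trial misses its stated power throughout.
- **Pilot status.** The plan says that it is not powered for small effects. That limits the weight of any power shortfall, but it does not argue for the wider of two available intervals.

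What the reply leaves standing is that the interaction is the only quantity called of interest, and that the better form is an unranked option.

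**Conclusion.** The point holds for continuous outcomes. The effect of interest in the general mixed model is, under pre/post coding, a change-from-baseline contrast. Its variance is 82/60/43% above that of the baseline-adjusted mean of three follow-ups at ρ = .4/.5/.6, and a single-visit interaction has 43/33/25% more. At ρ = .4 or .5 the change contrast falls short of 80% power at d = .35 with 180 men, while the adjusted form exceeds 90% at every ρ in the plan.

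These figures assume an identity link, complete data, equal variance and equal correlation across visits, and no adjustment for the baseline outcome. They do not carry over exactly to counts, binary outcomes, a linear time trend, or a model with the random slope that the plan says it may explore. The weakness is a better option left unselected, not a wrong analysis: the change contrast is unbiased under randomisation.

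**What to change.** In the mixed-model text under Estimation of parameters for a subsequent R01, state which form is primary. Suggested wording:

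*For each continuous outcome, the primary effect is the difference between MEET-ME and NTHP in the mean of the 30-, 60- and 90-day values, adjusted for the baseline value of the same outcome, whether or not the arms differ at baseline. The model with baseline as a response and a treatment main effect is supportive.*

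The model can be fitted with baseline as a covariate and three responses, or with four responses and no treatment effect at baseline. The plan should say which. In Data Analyses, keep the average-change comparison and label it descriptive.

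The cost is wording only. Table 3 already schedules the outcome measures at baseline, and the adjusted model is already written out. The one drawback is a summary slightly less familiar than raw change. The choice should be fixed before outcomes by arm are seen.

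### No primary GLMM contrast is named for condom use or UAI, and Table 4's N=180 continuous figures match a four-visit mean that the plan does not test

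*Combined protocol and SAP*

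**What the plan says.** All places are in the combined protocol and SAP.

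- **Estimation of parameters for a subsequent R01.** The pilot will estimate key parameters with 95% intervals and also "test the primary null hypotheses at the" two-sided .05 level. On the first task it says: "Estimation of critical design parameters with point and confidence interval estimates will be considered highly important".
- **GLMM specification (same section).** On time, "The variable Visit can be coded in different ways depending upon how one wants to model the effect of time on the mean response"; the examples are a binary pre/post indicator, a linear 0-3 score and a categorical visit. The treatment-by-visit coefficients are the ones of interest, "measuring the difference in the rate of change in outcome across the two treatment groups at each visit". A different model follows conditionally: "If the baseline outcome measure is included as a part of the covariates on the right hand side of the" equation, only three responses remain and "we can look at average treatment effect across visits without including the" interaction. Links are "identity for continuous outcome, logit for binary outcome and natural log for count outcomes".
- **Data Analyses, opening paragraph.** Alongside descriptive summaries, arms are compared on change from baseline averaged over the three follow-ups. This is not called primary.
- **Power for primary analysis and Table 4.** The calculation uses four observations, baseline included, with SD 1. The text claims 80% power for d > .35 at rho .6. Table 4's N=180 column gives .33/.35/.37 at rho .4/.5/.6. The contrast powered is not named.

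HIV/STI testing is outside this point. It has a specific aggregate analysis: tested at least once during follow-up, by logistic regression.

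**The concern.** The listed options answer different questions: average change, rate of change, change at one visit, or follow-up level given baseline. They also differ in precision. A .05 test and a 95% interval mean little until one option is chosen, and choosing after the data are seen leaves the result open to selection.

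The pilot aim does not remove the problem, because the interval is the main product. Power for primary analysis uses the 95% interval to check that an externally chosen effect size lies inside it, and says that error margins will be adequate even with 20% attrition. Which margin is meant depends on the contrast. If Table 4 was derived for something the plan never tests, it cannot show whether the margin is adequate.

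**Working it through.** **Inputs.** Arms 120 and 60 (Phase 3, Recruitment); SD 1 and rho .4/.5/.6 (Table 4, Power for primary analysis); two-sided alpha .05, power .80; attrition 20% by day 90 (Phase 3, Recruitment). Assumption: compound symmetry, in line with the plan's random intercept.

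Let v = 1/120 + 1/60 = .025 and z = 1.960 + .8416 = 2.8016. Detectable d = z x sqrt(variance). Power at a given d = Phi(d/sqrt(variance) - 1.96).

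**1. Reproducing Table 4, N=180.** The variance of an arm difference in the four-visit mean is v(1+3rho)/4 = .01375/.01563/.01750. Then d = .329/.350/.371, which rounds to the printed .33/.35/.37. A mean of the three follow-ups only, v(1+2rho)/3, gives .343/.362/.379 and does not fit. As a supporting check, the same four-visit factor in a pooled two-proportion formula with control rate .40 gives odds ratios 1.936/2.022/2.107, against the printed 1.93/2.02/2.11.

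**2. The contrasts that the plan names, complete data.**

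| Contrast | Variance | Detectable d (rho .4/.5/.6) | Power at Table 4's d |
|---|---|---|---|
| One visit's interaction | 2v(1-rho) | .485/.443/.396 | 48/60/74% |
| Linear slope, as the baseline-to-day-90 difference | (9/5)v(1-rho) | .460/.420/.376 | 52/65/79% |
| Pre/post interaction | (4/3)v(1-rho) | .396/.362/.323 | 65/77/89% |
| Baseline-adjusted average | v[(1+2rho)/3 - rho^2] | .294/.286/.271 | 88/93/97% |

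In each row d is the arm difference that the contrast estimates. All four rows fall as rho rises, while Table 4 rises. Changing N or allocation rescales v and cannot reverse that direction. The adjusted average has .44/.80 = .55, .4167/.6667 = .625 and .3733/.5333 = .70 of the pre/post variance.

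**3. The text's d = .35 at rho .6.** Power is 70% for one visit, 74% for the slope, 86% for pre/post and 95% for the adjusted average. For the four-visit mean it is 75%, because Table 4 itself gives .37 at rho .6; .35 belongs to rho .5.

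**4. 20% attrition.** Same loss in both arms, missing at random. Two patterns bound the range: gradual (80% complete, 6.7% lost before each follow-up) and early (20% with baseline only). With k follow-ups the conditional variance is c_k = [1+(k-1)rho]/k - rho^2. Let F be 1 divided by the sum of (pattern share/c_k) over patterns with a follow-up. The adjusted variance is vF and the pre/post variance is v[F + (1-rho)^2].

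Example, early loss, rho .4: F = .44/.8 = .55. Adjusted variance = .01375, half-width 1.96 x .1173 = .230. Pre/post variance = .025 x .91 = .02275, half-width .296.

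| | rho .4 | rho .5 | rho .6 |
|---|---|---|---|
| Half-width, pre/post (SD) | .29-.30 | .26-.27 | .24-.25 |
| Half-width, adjusted (SD) | .22-.23 | .21-.22 | .20-.21 |
| Power at Table 4's N=140 d (.39/.41/.44), pre/post | 73-76% | 84-87% | 94-96% |
| Same, adjusted | 91-94% | 95-97% | 98-99% |

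The N=140 column is used because 180 x .8 = 144 completers. At d = .35 and rho .6 with attrition, pre/post has 80-83% power and the adjusted average 90-93%.

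**The case against.** **The plan does point somewhere.** It calls the interaction coefficients the ones of interest, and its opening analysis paragraph names average change over the follow-ups. That shows a direction. But the coding stays open, the GLMM text goes on to offer a model without the interaction, and the average-change comparison sits with descriptive summaries.

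**It is a pilot that disclaims power for small effects.** True, and this limits the consequence. The .05 tests are still promised, and the intervals are the stated product.

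**The stated 80% power might be thought to hold for no named analysis.** A reader might infer this, but it is too strong. At d = .35 and rho .6, pre/post and the adjusted average both reach 80%, even after attrition. Nor do the figures show a general shortfall from attrition: against Table 4's N=140 column, pre/post misses 80% only at rho .4. The documents do not label that column an attrition scenario, but it is the nearest.

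**AIC/BIC might be thought to choose the visit coding and so inflate type I error.** The sentence "Models will be compared according to information criterion like AIC, BIC" follows those on the random slope and on maximum likelihood, and does not clearly refer to the coding. This point does not rest on it.

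**The four-visit reading of Table 4 is a reconstruction.** The formula and software are not stated. Under exact 2:1 it gives .373/.397/.420 at N=140 (printed .39/.41/.44) and .348/.371/.393 at N=160 (printed .35/.38/.40). Those columns fit only with assumed splits of 100:40 and 110:50. The match is therefore claimed for N=180 alone. The rise with rho is the firmer evidence.

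**Conclusion.** The point holds in this form. No contrast is designated primary for condom use or UAI partners and occasions, and Table 4's continuous N=180 row belongs to a quantity that includes a pre-treatment measurement and is not tested. If arms were equal at baseline and differed by Table 4's d at every follow-up, even that four-visit mean would have only Phi(.75 x 2.8016 - 1.96), about 56% power.

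The mismatch runs both ways. Table 4 is optimistic for the single-visit and slope forms at all three correlations and for pre/post at rho .4 and .5. It is conservative for pre/post at rho .6 and for the adjusted average throughout. The text's d > .35 at rho .6 also disagrees with Table 4.

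The sizes assume SD 1, compound symmetry, 120:60 arms and, with attrition, equal loss missing at random. They apply to continuous outcomes. UAI is labelled continuous under Outcome indicators, while the GLMM text provides a log link for counts. Table 4 has no count row, and no magnitude is claimed here for UAI counts. This should be corrected, but it does not undermine the trial's feasibility aims.

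**What to change.** Before unblinded data are seen:

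1. Designate the plan's own baseline-adjusted model as primary for condom use and for UAI partners and occasions: follow-ups as responses, the baseline value of the same outcome as covariate, and the treatment effect averaged over a follow-up window fixed in advance. Use the log link for UAI counts.
2. Make the pre/post, linear and per-visit interactions secondary.
3. State that AIC/BIC serves only to choose the random-effects or covariance structure.
4. Recompute Table 4 and the d > .35 statement for that contrast, with arm sizes stated and 20% attrition included. With all three follow-ups, the detectable d at rho .4/.5/.6 would be .29/.29/.27 with complete data and .31-.33/.30-.32/.29-.30 with attrition. UAI counts need their own calculation.

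The cost is SAP wording and a recomputed table. Table 3 already collects sexual behavior at baseline and every follow-up.

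There are two trade-offs. Participants with no follow-up do not contribute to this model, so report their number by arm and give the four-visit model, with baseline as a response, as a sensitivity analysis. The window is the investigators' choice, since the Phase 3 text says that participants may need time to apply the content. As illustration only, with 20% attrition and rho .4-.6, an assumed effect of 0/.25/.50 SD gives 57-69% power for the three-visit average and 82-91% for the 60/90-day mean. An assumed constant .35 SD gives 85-93% and 77-87%. Neither pattern comes from the documents.

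### Continuous outcomes: the base model is a random intercept with an AIC/BIC slope check that has no deciding rule; if correlation falls with time and the intercept is kept, some Trt × Visit tests exceed 5% (minor, nearly free to fix)

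*Combined protocol and SAP*

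**What the plan says.** All references are to the Data Analyses part of the combined protocol and SAP, unless another section is named.

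- **Base model.** The longitudinal model is a GLMM with an identity, logit or log link. Its subject-specific random intercepts "are assumed to be normally distributed with a common variance and they account for within-person correlation".
- **Extension.** The next sentence reads "We will also explore if we need a subject specific random-slope corresponding to visit in the above model". Candidate models are then compared by criteria such as AIC and BIC. Neither is named as decisive.
- **Robustness.** The plan adds a GEE: "we will also apply an exchangeable working correlation structure". It does not say that sandwich standard errors will be used. The sentence follows the collapsed analysis of HIV/STI testing and may refer only to that outcome.
- **Target.** The Trt × Visit coefficients are named as the terms of interest. Visit may be coded pre/post, as a linear 0-3 trend, or as categories. A baseline-adjusted average effect over the three follow-ups, without the interaction, is offered as an alternative.
- **Level.** Estimation of parameters for a subsequent R01 promises 95% intervals, "and test the primary null hypotheses at the" "traditional two-sided level" of .05.

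**The concern.** With independent residuals of constant variance, a random intercept gives every pair of visits the same correlation. Suppose the true correlation falls as the gap widens. The model-based standard error is then too small for contrasts that lean on distant visits (the linear trend, and baseline to day 90) and too large for baseline to day 30. Tests and intervals for the terms of interest would be miscalibrated in a direction that depends on the Visit coding.

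Intervals matter more than p-values here. The plan treats interval estimates of design parameters as highly important, and Power for primary analysis uses 95% intervals to exclude extreme effects before the next trial. A random slope can absorb falling correlation, but whether it enters the model depends on a comparison with no stated rule.

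**Working it through.** **Inputs from the documents**
- Two-sided 5% level (Estimation of parameters for a subsequent R01).
- Sample: "N=180 (MEET-ME, n=120; NHTP, n=60" (Phase 3 Recruitment).
- Design: "using a repeated measures group design (N=180) with 4 observations (baseline + 3 FUs", with SD 1 (Power for primary analysis).
- Common within-subject correlation of .4, .5 or .6 (Table 4, headed "Detectable Effect (.80 power, alpha=.05").

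**Assumed, not in the documents:** correlations of .6, .5 and .4 at gaps of 30, 60 and 90 days, with milder alternatives in step 4. Outcomes are normal and data complete, so the projected 20% attrition is not modelled.

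**Step 1. Reproduce Table 4 (continuous, N = 180).** For a time-averaged difference with m = 4:

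d = (1.96 + 0.842) × √[(1/120 + 1/60) × (1 + 3ρ)/4]

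- ρ = .4: 2.802 × √(.025 × .550) = .329 (stated .33)
- ρ = .5: 2.802 × √(.025 × .625) = .350 (stated .35)
- ρ = .6: 2.802 × √(.025 × .700) = .371 (stated .37)

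The table reproduces. It uses one common ρ per row and describes a time-averaged effect, not a Trt × Visit slope.

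**Step 2. True and model-based variance.** For a within-person contrast c, the true variance is proportional to c′Vc, where V is the true correlation matrix. The random-intercept model uses (1 − ρ̄) × c′c, where ρ̄ is the mean of the six pairwise correlations. The factor (1/120 + 1/60) cancels.

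ρ̄ = (3 × .6 + 2 × .5 + .4)/6 = .533

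Linear contrast (−3, −1, 1, 3), with c′c = 20:
- True: 20 + 2 × (5 × .6 − 6 × .5 − 9 × .4) = 12.8
- Model: 20 × .467 = 9.33
- Ratio: 12.8/9.33 = 1.371

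Baseline to day 90: true 2 × (1 − .4) = 1.2; model 2 × .467 = .933; ratio 1.286.

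**Step 3. Actual error with the random intercept kept.** Error = 2 × [1 − Φ(1.96/√ratio)]. The last column comes from 2,500 simulated trials; its standard error is √(.05 × .95/2500), about 0.4 points, at a true 5%, and about 0.6 at 10%.

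| Test at .6/.5/.4 | Ratio | Formula | Simulated |
|---|---|---|---|
| Linear Trt × Visit | 1.371 | 9.4% | 9.8% |
| Baseline to day 90 | 1.286 | 8.4% | 8.8% |
| Pre/post | 1.143 | 6.7% | 6.6% |
| Baseline to day 60 | 1.071 | 5.8% | 6.2% |
| Baseline to day 30 | 0.857 | 3.4% | 3.8% |
| Joint 3-df Trt × Visit | – | – | 5.7% |
| Baseline-adjusted average effect | 1.00 | 5.0% | – |

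Other runs put the linear test at 10.5% and 11.1%. Interval width relative to the correct width is 1/√1.371 = .854 (linear) and 1/√1.286 = .882 (day 90), so these intervals are about 15% and 12% too narrow.

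**Step 4. Milder decay, random intercept kept.**

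| Correlations | Linear | Day 90 |
|---|---|---|
| .55/.5/.45 | 7.1% | 6.6% |
| .6/.55/.5 | 7.4% | 6.8% |
| .5/.45/.4 | 6.9% | 6.5% |

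**Step 5. With the planned slope check.** At .6/.5/.4, the 2,500-trial run gave 5.4% (linear) and 5.6% (day 90) after AIC choice, and 6.2% and 6.0% after BIC choice. A smaller run of 1,000 trials gave 6.4% (AIC) and 7.0-7.5% (BIC) for the linear test. Over all runs the range is about 5-7% with AIC and 5-8% with BIC.

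How often the slope was added:

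| Setting | AIC | BIC |
|---|---|---|
| .6/.5/.4, linear | 98-99% | 68-83% |
| .55/.5/.45 and .6/.55/.5 (linear and day 90) | 57-70% | 5-25% |
| .6/.5/.4, pre/post | – | 4-9% |

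Much of the BIC spread in the first row comes from whether its penalty counts 180 × 4 = 720 observations or 180 men, which the plan does not state. Under the milder .55/.5/.45, error after BIC choice was about 6-7%.

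**Step 6. GEE.** With sandwich standard errors, the exchangeable GEE ran at 5.4% (linear) and 5.7% (day 90) at .6/.5/.4.

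**The case against.** The strongest reply is that the plan already contains the remedy. A random slope is considered immediately after the random intercept is described, and at .6/.5/.4 AIC almost always adds it. A reader might infer from step 3 that the planned tests run at 8-10%. The documents do not support that, because it describes an analysis that skips a written step. This part of the reply stands.

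Second, the decay is assumed. A reader might take Table 4's .4 to .6 as evidence that correlation falls over follow-up. Those are alternative values of one common correlation, and assigning .6 to the 30-day gap and .4 to the 90-day gap is the steepest linear fall that the range allows. This stands too.

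Third, the inflation is not general. It is largest for the linear and 90-day tests, absent for the baseline-adjusted average effect, and reversed at day 30. The figures cover only the identity link with complete data. The collapsed logistic analysis of testing has no repeated-measures correlation to misspecify.

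Fourth, the exchangeable GEE might be read as part of the problem. With sandwich errors it is not; the gap is only that the plan does not state them.

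Finally, this is a pilot whose main role is parameter estimation, and it declines to take effect sizes from pilot data. That lowers the stakes without removing them, since its intervals are still meant to rule out extreme effects.

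What the reply leaves open is the missing decision rule. The slope is only explored, AIC and BIC can disagree, and BIC usually keeps the intercept-only model under mild decay or pre/post coding.

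**Conclusion.** A minor point holds. The plan fixes no covariance structure for continuous outcomes. Its base model assumes equal correlation between all visits, and the step that could relax this has no governing criterion.

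The size is conditional. With the random intercept kept and correlation falling from .6 to .4, the linear test runs at about 9.4%, the 90-day contrast at 8.4%, pre/post at 6.7% and the 30-day contrast at 3.4%. Milder decay gives about 7% for the linear and 90-day tests. With the slope check done, error is about 5-7% (AIC) or 5-8% (BIC). If correlation is constant over time, there is no excess at all.

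These figures rest on assumed decay, normal outcomes and complete data. They should not be carried over to the logit or log models.

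**What to change.** - **Continuous outcomes.** State that the four visits will be modelled with an unstructured covariance, in place of the random intercept and the AIC/BIC choice of random effects. This makes no equal-correlation assumption and works under any of the listed Visit codings.
- **Binary and count outcomes.** State that tests and confidence intervals use robust (sandwich) standard errors with a small-sample correction, and that this applies to the GEE.

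The cost is a sentence or two in Data Analyses and no new data. An unstructured covariance has 4 × 5/2 = 10 parameters, against 2 for the random-intercept model (intercept and residual variance). That is affordable with 180 men.
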